**Analysis Plan**

Sample Size: Sample size calculations are based on our ability to detect a medium effect size (d) of 0.45; and d) a type I error rate of .05. Our projected effect size is justified for two reasons. First, clinical trials on symptoms of CRD use this effect size as an indication of clinical significance. Second we were able to achieve large treatment effects across outcomes in the pilot phase- although we acknowledge that effect sizes may be overly optimistic in pilot studies. To attain 80% power for a two-sided comparison of the two treatment groups at 1 month will require 78 dyads per group (Aim 1 and 2). We plan to recruit an additional 22 per group or 100 dyads for a total of 200 allowing for 22% attrition by 4 months (Aim 3). The statistical power for secondary analyses at 3 months will be the same as for the primary; 80% for a 0.45 effect size with 5% two-tailed tests. Analysis of aims: First, we will conduct

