descriptive analyses and univariate comparisons of the experimental and control intervention group conditions. We will use Chi-square, Wilcoxon rank-sum tests, and independent groups t-tests as appropriate to identify any differences between experimental and control group participants at baseline. In addition to serving as a final data quality check, these analyses will be used to characterize our study population, assess the success of randomization in balancing the two groups and determine the impact of any dropouts on group balance. Aim 1: to test the timed activity intervention on patient CRD symptoms and QOL. Our primary analysis will examine the effect of the timed intervention compared to the attention control condition based on "intention to treat" (ITT). Data from all dyads randomized to the experimental group will be part of analyses regardless of actual number of completed intervention sessions. We will test the normality assumption for the primary CRD outcome measure (WASO) and for the other dependent measures (TST, neuropsychiatric symptoms; QoL) by examining the distribution of residuals after standard parametric comparisons. If the residual distribution is markedly skewed, we will examine whether data transformations are sufficient for improving the fit of the data to the normality assumption. Aim 1: To analyze the effects of the timed intervention on our primary outcomes difference scores (T2-T1) will be calculated for each participant and these change scores will be analyzed as a function of the treatment group, with the baseline observation (T1) serving as a covariate. Other potential covariates measured at baseline (e.g., age, education) will also be evaluated as potential predictors of change in outcome, and included as additional covariates of the intervention effect as indicated. Aim 2: To test the effect of the timed activity intervention on caregiver outcomes. For Aim 2, we follow the approach for Aim 1 by examining group differences in the baseline-adjusted change scores (T2-T1; T3-T1) for CG outcome measures of burden and intent to institutionalize. Aim 3: To test the mediating effect of patient HPA axis activity on symptoms of CRD. We will test mediation by modeling the measures of baseline-adjusted changes in CRD symptoms (WASO, TST, neuropsychiatric symptoms) in nested analytic models that either do or do not include the proposed mediator (T2-T1 change in saliva cortisol). Using nested regression models, estimates will be obtained of 1) the effect of the intervention on baseline-adjusted change in cortisol, 2) the effect of the change in cortisol on baseline-adjusted change in WASO (or other outcomes), 3) the effect of the intervention on baseline-adjusted WASO before adding change in cortisol to the model, and 4) the effect of the intervention on baseline-adjusted WASO after adding change in cortisol to the model. These path estimates are often referred to by the letters a, b, c, and c' in the mediation literature. The product of the a and b estimates (a\*b) represents the mediated effect, and this will be tested for statistical significance using the standard Sobel method or with bootstrapping techniques. The proportion of the total effect (c) that is explained by mediation (a\*b) will also be calculated and tested for significance. Mediation models for data from two-wave randomized trials can provide substantially different results depending on whether change scores are used and whether baseline covariate adjustments are implemented. Our approach will capitalize on this recent methodological work and provide sensitive analyses that determine whether the interventions impact on 1-month change in CRD symptoms is partly due to its effect on 1-month change in cortisol secretion.

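### Aim 3: the plan does not put baseline cortisol in the b and c' models, so the mediated effect is biased in either direction unless WASO depends on cortisol only through its change

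*Combined protocol and SAP*

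**What the plan says.** The Analysis Plan describes Aim 3 in words, without equations. It compares "nested analytic models that either do or do not include the proposed mediator (T2-T1 change in saliva cortisol"). Four estimates follow. Path a is "1) the effect of the intervention on baseline-adjusted change in cortisol". Path b is "2) the effect of the change in cortisol on baseline-adjusted change in WASO (or other outcomes"). The last two are the intervention effect on baseline-adjusted WASO before (c) and after (c') the cortisol change enters the model. The product a*b is tested by the Sobel method or by bootstrapping, and the share of c that it explains is reported.

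Aim 1 in the same section shows what baseline adjustment means: "change scores will be analyzed as a function of the treatment group, with the baseline observation (T1) serving as a covariate". On that usage, path a carries T1 cortisol, and the b, c and c' models carry T1 WASO. T1 cortisol is named for no outcome model.

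The section also notes that two-wave mediation results depend on the use of change scores and baseline covariates, and says that the approach will draw on recent methodological work. It does not say which covariates the b and c' models will hold.

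**The concern.** The mediator is a T2-T1 change. People with high T1 cortisol tend to show falls and people with low T1 cortisol tend to show rises, so the change carries information about the starting level. If T1 cortisol predicts later WASO in its own right and is left out of the outcome model, part of that association is credited to the change. Path b is then confounded, and a*b and the proportion mediated inherit the error.

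Aim 3 is a stated specific aim and carries the trial's claim about mechanism. Either error matters: reporting cortisol as the mechanism when it is not, or missing it when it is.

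**Working it through.** **The plan's own figures.** The plan gives no calculation for the mediation test, so only the group size can be reproduced. Inputs: "our ability to detect a medium effect size (d) of 0.45", "a type I error rate of .05", and "To attain 80% power for a two-sided comparison of the two treatment groups at 1 month will require 78 dyads per group".

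- n per group = 2 × (1.960 + 0.842)² / 0.45² = 77.5, so 78. This agrees.
- 78 / (1 - 0.22) = 100 per group. This agrees with "for a total of 200 allowing for 22% attrition by 4 months (Aim 3").

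I use 78 per arm (156 dyads) below.

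**Algebra.** Let M1 and M2 be cortisol at T1 and T2, D = M2 - M1, and ρ the T1-T2 cortisol correlation. Take b from the model that also holds arm and T1 WASO. Given those two, suppose T2 WASO depends on cortisol as

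b·M2 + g·M1 = b·D + (b + g)·M1,

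where g is the direct effect of T1 cortisol. Leaving out M1 adds (b + g) times the within-arm slope of M1 on D. With equal variances at T1 and T2, and M1 uncorrelated with T1 WASO, that slope is (ρ - 1)/(2 - 2ρ) = -1/2, whatever ρ is. So

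fitted b → b - (b + g)/2 = (b - g)/2.

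The bias is zero only if g = -b, that is, if WASO depends on cortisol only through D.

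If T1 cortisol and T1 WASO correlate at 0.2 and ρ = 0.5, the slope is -(0.5 × 0.96)/(0.25 × 0.96 + 0.75) = -0.48/0.99 = -0.485. Then b = 0, g = 0.3 gives a fitted b of -0.145, and b = 0.30, g = 0 gives 0.30 - 0.145 = 0.155.

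**Simulation.** Every input here is an assumption: ρ = 0.5, arm effect on cortisol a = 0.45 SD (the plan's d of 0.45 is not stated for cortisol), T1 cortisol-WASO correlation 0.2, T1-T2 WASO slope 0.5, residual SD 0.8. There were 1,500 trials per scenario (600 for the percentile bootstrap). Ranges show separate runs.

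False mediation, true b = 0:

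| g | mean fitted b, T1 cortisol out | Sobel, out | Sobel, in | Bootstrap, out | Bootstrap, in |
|---|---|---|---|---|---|
| 0 | 0.00 | 1.5% | 1.5% | not run | not run |
| 0.1 | -0.05 | 4-5% | 1-2% | 11.5% | 5.8% |
| 0.2 | -0.10 | 13-14% | 1-2% | 25.7% | 4.5% |
| 0.3 | -0.15 | 30-31% | 1-2% | 50.0% | 3.5% |

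Sensitivity, Sobel with T1 cortisol out:

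- ρ from 0.3 to 0.7, g from 0.1 to 0.3: 4% to 38%. With a = 0.8 SD: 7% to 63%.
- a = 0.2 SD, g = 0.3: 5.6%.
- a = 0: at most 1.1%, because a*b stays near zero.
- 100 per arm (ρ = 0.5, a = 0.45): 6.7%, 22.9% and 46.7% for g = 0.1, 0.2 and 0.3. A larger sample makes it worse, as expected of bias.

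True mediation, b = 0.30:

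| g | mean fitted b, out | Sobel power, out | Sobel power, in |
|---|---|---|---|
| 0.2 | 0.06 | 4% | 77% |
| 0 | 0.16 | 34-35% | 77-78% |
| -0.3 (change only) | 0.30 | 83-85% | 77-79% |
| -0.5 | 0.40 | 87% | 78% |

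At g = 0, mean a*b is 0.07 where the truth is 0.45 × 0.30 = 0.135. At g = -0.5 it is overstated (0.18). Bootstrap power at g = 0 is 53.8% without T1 cortisol and 88.7% with it.

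**The case against.** The strongest reply is that the plan is silent and does not exclude T1 cortisol. It gives no equations, path b's cortisol change could refer back to the adjusted change in path a, Aim 1 allows further baseline covariates as indicated, and the section recognises that baseline adjustment matters. This stands in part: a reader might infer a deliberate exclusion, and the text does not support that. But T1 cortisol is attached to one model only, the optional covariates belong to Aim 1 and do not guarantee it, and a general promise to follow recent methods fixes no model.

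The second reply is that Hypothesis 3 (Overall objectives) makes cortisol change itself the mediator, which is the case without bias. It stands as a condition. Naming change as the mediator does not ensure that starting level has no association of its own with later WASO, and nothing in the documents commits to that.

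Three stronger readings are tempting and are not supported:

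- That a*b is biased in any event. It is not when g = -b.
- That the analysis will declare mediation falsely. That needs a real arm effect on cortisol and a sizeable g. At g = 0.1 or a = 0.2 SD the Sobel rate is only about 5%.
- That a and b refer to different mediators. Randomisation makes T1 cortisol independent of arm, so a has the same expectation with or without adjustment. The defect lies in b.

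**Conclusion.** The concern holds in conditional form. As described, the b and c' models leave out T1 cortisol, and b then tends to about (b - g)/2 under equal cortisol variances, with the error passed on to a*b and the proportion mediated. The direction cannot be known in advance. Under the assumed inputs, false mediation by the Sobel test reaches about 31% at g = 0.3, and power for a true b of 0.30 acting through T2 level falls from about 77% to 34%. Bootstrapping does not help, because the estimate itself is off. The sizes rest on values of g, ρ and a that the documents do not give; the algebra needs only the equal-variance and correlation assumptions stated with it. The treatment comparisons of Aims 1 and 2 and the sample size are not touched. The change should be made, but it does not bear on the primary result.

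**What to change.** In the Aim 3 text of the Analysis Plan, write out the three regressions before the mediation data are analysed:

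- a: cortisol change on arm, T1 cortisol and the T1 value of the outcome.
- b and c': outcome change on arm, cortisol change, T1 cortisol and the T1 value of the outcome.
- c: as for b and c', without cortisol change.

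Fit all three on the same dyads (cortisol at both times and the outcome at both times), and compute a*b and the proportion mediated from them. With the same covariates and the same dyads, least squares gives c = c' + a*b exactly, so the proportion is coherent.

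The cost is a few lines of text and one degree of freedom in the outcome model. No new data are needed: Study Instruments already has saliva collected before the first visit and after the last intervention visit. If the effect runs purely through change, Sobel power falls a little, from about 85% to 79% (83% to 77% in a second run).

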All measures to be used in the study are established indexes. No new or novel instruments will be used. Quality of life in persons with dementia will be assessed using two well established measures the QOL-AD and the PHQ-9. The dementia-specific 13-item Quality of Life in Alzheimer's Disease scale reflects multiple dimensions (physical, social, emotional, and functional well-being) with each rated as 1=poor, 2=fair, 3=good, or 4=excellent. A total score representing the sum of items ranging from 13 to 52 will be derived separately for persons with dementia and the family caregivers (CG). In addition, CG will be asked to complete the PHQ-9. Persons with dementia will be administered the MMSE. Other instruments include the MMSE, the Barthel Index, Cognitive status will be measured at baseline using the Mini Mental State Exam (MMSE) Physical function will be measured at baseline using the Barthel Index. Neuropsychiatric symptoms will be measured using the Neuropsychiatric Inventory (NPI) Sleep disturbance will be assessed using the PROMIS Sleep Related Impairment index. Neuroendocrine activity in persons with dementia will be assessed using the biological signature of the HPA response via salivary cortisol. CG will be instructed to collect assays at the awakening challenge and at 3 additional intervals (30 minutes after waking, mid day, and at bedtime one hour after dim light exposure). Caregivers will be provided all materials and marked plastic bags to freeze samples until pick up by the trained data collector. Caregivers will be asked to collect saliva for 2 consecutive days prior to the first study visit, and again after the last intervention visit. Sleep-wake activity will be measured using an actigraphy bracelet worn by the person with dementia. The Motionlogger actigraph, which is manufactured by AMI and utilize the same algorithm as used in earlier studies of community dwelling persons with dementia, will be placed on the non-dominant wrist at baseline and will be worn for consecutive 24 h-periods until removal at 1 month (T2) data collection. Actigraphs will be set to collect data in 60-second epochs via tri directional accelerometer using a validated algorhythm. The primary measure of interest will be number of minutes of wake after sleep onset (WASO). Other parameters that will also be subject to analysis include total sleep time (TST), day/night sleep ratio, and number of night awakening. There will NOT be any remote monitoring or data transfer with the actigraph through a wireless connection.

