Once eligibility is determined and consent is signed, dyads of persons with dementia and their caregivers will receive a baseline home interview (T1). Following the baseline interview, participants will be randomly assigned to experimental or attention-control group conditions. Experimental dyads will receive up to 8 contacts with a interventionist over 1-month. The attention-control group dyads will receive comparable attention in a structured program involving the same number and mix of in-home and telephone contact as the treatment group. All dyads will be retested at 1-month from baseline (T2) to evaluate proximal outcomes of neuropsychiatric symptoms, QOL, and sleep quality and at 4 months (T3) to evaluate sustained uptake and distal outcomes of QOL and other measures of satisfaction with the study procedures. Outcome measures will be assessed by interviewers masked to treatment assignment. In addition, participants will be asked about their experience with the COVID-19 pandemic (using the University of Pittsburgh COVID Caregiving Questionnaire) at T3. This data will be collected via telephone only. The only information collected will include their answers to the questions on the survey and their de-identified participant number.

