## Objectives

### Overall objectives

We propose a definitive Phase III efficacy trial of the Healthy Patterns intervention, designed to improve sleep disturbance symptoms and QOL, that systematically builds on our pilot work demonstrating feasibility, safety and potential benefits. We will use a randomized, two-group, parallel design of 200 persons with dementia (PWD) and their family caregivers (dyads) assigned to the Healthy Patterns intervention or an attention control intervention of equivalent in-home attention and social contact. Specific components of this brief, one-month, eight session, home-based intervention include: 1) assessing PWD health/functional status and preferences/interests; 2) educating caregivers on environmental cues to promote activity and sleep; and 3) training of CG in using timed morning, afternoon, and evening activities based on circadian needs across the day. The patient focused outcomes of interest are QOL, and indices of sleep as measured by objective and subjective indicators including actigraphy, subjective sleep quality, and assessment of neuropsychiatric symptoms. Caregiver outcomes of interest are QOL, burden, confidence using activities, and sleep disruption. The specific aims for this study are to test: 1. The immediate (at 1 month) and sustained (at 4 months) effect of the Healthy Patterns activity intervention on PWD quality of life and CRD symptoms. Hypothesis 1a. Compared to control group participants, PWD receiving the intervention will demonstrate quality of life, total sleep time, nocturnal wake after sleep onset, day/night sleep ratio, and neuropsychiatric symptoms at 1 month. Hypothesis 1b. Compared to control group participants, PWD subjects receiving the intervention will demonstrate quality of life, total sleep time, and neuropsychiatric symptoms at 4 months. 2. The immediate (1 month) and sustained (4 months) effect of the Health Patterns activity intervention on caregiver outcomes. Hypothesis 2a. Compared to control group participants, caregivers who have received the intervention training will demonstrate quality of life, burden, confidence in using activities, and sleep disruption at 1 month. Hypothesis 2b. Compared to control group participants, caregivers who have received the intervention training will demonstrate quality of life, burden, confidence in using activities, and sleep disruption at 4 months. 3. The mediating effect of neuroendocrine activity on changes in CRD symptoms. Hypothesis 3. CRD symptoms will be mediated by changes in diurnal cortisol from baseline to 1 month.

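### Aim 3 cannot determine that the intervention works through cortisol: the cortisol-to-symptom path is not randomised, and the plan has no safeguard against a shared cause

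*Combined protocol and SAP*

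**What the plan says.** Hypothesis 3 (Overall objectives) states that "CRD symptoms will be mediated by changes in diurnal cortisol from baseline to 1 month". For Aim 3, the Analysis Plan takes as mediator "the proposed mediator (T2-T1 change in saliva cortisol") and fits nested regressions. One of them estimates "the effect of the change in cortisol on baseline-adjusted change in WASO (or other outcomes"). The product a*b is tested by the Sobel method or by bootstrap, and the proportion mediated is reported. The section closes by saying that the analyses will determine whether the intervention's impact on "1-month change in CRD symptoms is partly due to its effect on 1-month change in cortisol secretion".

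Cortisol and outcome changes are both baseline-adjusted. The plan notes that results can depend on the choice between change scores and baseline adjustment. For Aim 3 it names no other covariates, and it does not discuss confounding of the mediator with the outcome.

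On timing, Study Instruments says caregivers are "asked to collect saliva for 2 consecutive days prior to the first study visit, and again after the last intervention visit", and that the actigraph "will be worn for consecutive 24 h-periods until removal at 1 month (T2) data collection".

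**The concern.** Arm is randomised, but cortisol change within arm is not. The a path (arm to cortisol) and the total effect c (arm to symptoms) are therefore protected by design, and the b path (cortisol to symptoms) is an observational association. Both variables are changes over the same month. Anything that moves both in the same people produces a non-zero b even if cortisol does nothing to sleep or behaviour; intercurrent illness or a change in household stress are examples. If the intervention also shifts cortisol, a*b is then non-zero and the test can declare mediation.

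Mechanism is one of the three aims, and the Design and Procedures sections repeat it as a purpose of the trial. The risk is a published claim that the programme works through the HPA axis when the data show only that two changes went together.

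**Working it through.** **The plan's own figure.** For d = 0.45, two-sided 0.05 and 80% power, n = 2(1.96 + 0.842)²/0.45² = 77.5, so 78 per group. Allowing for 22% attrition, 78/0.78 = 100. Both reproduce and neither is disputed; 78 per group is used below.

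**Assumptions not in the documents.** The residual correlation r between cortisol change and WASO change, the arm effect on cortisol, and a T1-T2 correlation of 0.5 are all assumed. The plan's 0.45 is its sample-size effect for the 1-month comparison. It is used here as the arm effect on WASO; nothing is stated for cortisol.

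**Shared cause, true b = 0.** Work in residual SD units.
- The estimate of a centres on the arm effect on cortisol, with SE(a) = √(2/78) = 0.160.
- The estimate of b centres on r instead of 0, with SE(b) ≈ √((1 − r²)/156).
- Sobel z = ab/√(a²SE(b)² + b²SE(a)²).

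With a = 0.45:
- r = 0.2: SE(b) = 0.078, ab = 0.090, z ≈ 0.090/0.0477 = 1.89.
- r = 0.3: SE(b) = 0.076, ab = 0.135, z ≈ 0.135/0.0591 = 2.29.

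The typical statistic thus sits near or above 1.96 although cortisol has no effect. The Sobel statistic is not normal at this size, so rejection rates come from simulation (thousands of trials per scenario). Ranges show the spread between repeat runs.

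| Arm effect on cortisol | r = 0.2 | r = 0.3 |
|---|---|---|
| 0.45 SD | 33–34% | 62–63% |
| 0.3 SD | 13–14% | 30% |
| 0.2 SD | 5–6% | 14% |
| 0 | about 1% | 1–2% |

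As a hand check at a = 0.45 and r = 0.2, the chance that a is significant is 0.80 and that b is significant is 0.72. The product is 0.58, against 0.55 simulated for both paths being significant. The bootstrap option behaves much like this joint test: it gave 53–56% at r = 0.2 and 78–79% at r = 0.3, so the table's Sobel rates are the lower of the plan's two options.

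**Comparison with true mediation.** When the arm acts on WASO only through cortisol, with a = 0.45, Sobel is significant in 33% of trials at r = 0.2 and 64% at r = 0.3. These are nearly the shared-cause rates, so the test result does not tell the two structures apart.

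**Reverse direction (arm to WASO, WASO to cortisol).** Here a is only 0.45r: 0.09, 0.135 and 0.225 at r = 0.2, 0.3 and 0.5. The chance that a is significant is then 8%, 13% and 29%. Sobel declares cortisol mediation in about 1–2%, 7% and 24–26% of trials.

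**The case against.** **Arguments that stand in part**
- The plan is not bare. It adjusts both changes for baseline, and Aim 1 evaluates other baseline covariates such as age and education, which could naturally be carried into Aim 3.
- Eligibility removes several common causes. The Key exclusion criteria cover drugs affecting HPA measurement, sedatives or hypnotics, Cushing's and Addison's disease, recent surgery and bereavement. The Key inclusion criteria require 90 days of stable psychotropic dosing.
- This makes a small r more plausible. It does not address causes arising during the month, and Aim 3 itself names no covariates beyond baseline.
- The limitation is common to two-wave mediation designs, and the Aim 1 and Aim 2 comparisons are unaffected.

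**Stronger readings that the documents do not support**
- *That cortisol is sampled only once the WASO nights are over.* Study Instruments places the second saliva collection after the last intervention visit, while the actigraph stays on until T2. The two may overlap, and the nights that form T2 WASO are not defined. The point rests on the shared T1-T2 window and the unrandomised b path, not on this order.
- *That a significant a*b arises equally under reverse causation.* The rates above are much lower, and below 5% at r = 0.2.
- *That the false-claim rate is high whatever the cortisol effect.* It falls to about nominal or below when the arm barely moves cortisol and r is modest.

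**Conclusion.** The point holds as a limit on what Aim 3 can conclude. The planned analysis can show a pattern consistent with mediation; it cannot determine that the CRD effect is partly due to cortisol.

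If a shared cause gives a residual correlation of 0.2 to 0.3 and cortisol has no effect, the Sobel test declares mediation in roughly 5–14% of trials for a 0.2 SD arm effect on cortisol, 13–30% for 0.3 SD, and 34–63% for 0.45 SD. Reverse causation is a smaller threat: about 1%, 7% and 24% at r = 0.2, 0.3 and 0.5. All these rates depend on assumed correlations and cortisol effects. The structural conclusion does not.

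A reader might infer that the mediation aim is worthless or that the efficacy results are compromised. Neither follows: a and c remain randomised comparisons. This is a cheap and worthwhile correction to a mechanistic aim.

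**What to change.** In the Aim 3 section:
1. In the b-path model, keep baseline cortisol and the baseline outcome, and add named baseline factors already collected: age, MMSE, Barthel Index and medication use.
2. Pre-specify a sensitivity analysis that reports the mediator-outcome residual correlation at which a*b becomes zero. In these linear models that is the observed partial correlation of the two changes given arm and the baseline covariates, so readers can judge whether a shared cause of that strength is plausible.
3. Replace the promise to determine causation with an aim to assess whether the data are consistent with mediation. Keep that wording whatever the supporting analyses show.

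Optional support: relate T1-T2 cortisol change to neuropsychiatric symptoms at T3, adjusted for their T2 value. First confirm that they are collected then: Hypothesis 1b lists them at 4 months, but the T3 description under Administration of Surveys and/or Process does not. This is not possible for WASO, because actigraphy stops at T2. A reverse model may be shown as description but does not settle direction: under a pure shared cause with equal arm effects it was significant as often as the forward model (33% and 63% at r = 0.2 and 0.3).

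The cost is a little more analysis on data already planned, and a more modest mechanism claim. No new visits or participants are needed.
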